## **4.5 SAFETY ANALYSES**

### **Safety Endpoints (Primary Objective)**

The primary objective for this study is to compare the safety of a single dose of baloxavir marboxil with 5 days of oseltamivir administered twice daily. The safety population will be used for all safety analyses. Patients will be analyzed according to the treatment they actually received.

The safety of baloxavir marboxil will be evaluated for adverse events, vital signs measurements, and clinical laboratory tests. Safety parameters will be summarized or listed for the safety population.

#### **4.5.1 Adverse Events**

AEs will be classified by system organ class (SOC) and preferred term using Medical Dictionary for Regulatory Activities (MedDRA) Version 22.0 and adverse event severity will be graded according to National Cancer Institute Common Terminology Criteria for Adverse Events (NCI CTCAE) v5.0 or the Adverse Event Severity Grading Scale for events not specifically listed in NCI CTCAE toxicity grading scale ([Table 2](#) of the protocol) on the eCRF, AEs reported after the initial dose of the study drug will be used for safety analyses.

In summaries by SOC and preferred term (PT), AEs will be sorted by overall decreasing frequency within each SOC and PT.

#### **All Adverse Events**

Only treatment-emergent AEs will be summarized. Treatment-emergent events are defined as those AEs with observed or imputed onset date on or after the start date of trial treatment. Only where the most extreme intensity is greater than the initial intensity (or if most extreme intensity is not missing and initial intensity is missing) will events with an onset date prior to the start of study treatment be considered treatment-emergent. An AE with a completely missing start date will be assumed to be treatment-emergent unless the AE has a complete non-imputed end date that is prior to study Day 1.

Adverse events will be coded and tabulated by SOC and/or PT. In tabulations, PTs and their associated SOC will be presented in order of descending frequency summed across the treatment arms. Adverse events will also be tabulated by severity and relationship to the study drug as indicated by the investigator. Adverse events leading to withdrawal, AEs leading to death, and AEs leading to a dose modification or interruption will be summarized.

The following will also be summarized by treatment, and listings produced where required:

- Serious AEs
- AEs leading to withdrawal
- AEs leading to death
- AEs leading to a dose modification or interruption
- Non-serious AEs occurring in  $\geq 5\%$  of patients in at least one treatment group
- Non-serious AEs occurring in  $\geq 1\%$  of patients in at least one treatment group

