**Table 1 Objectives and Corresponding Endpoints**

Safety (Primary) Objective	Corresponding Endpoint

 
To compare the safety of a single dose of baloxavir marboxil with 5 days of oseltamivir administered twice daily
 
	
 
Incidence, severity, and timing of adverse events, serious adverse events, vital sign measurements, and clinical laboratory test results
 

Pharmacokinetic Objective	Corresponding Endpoints

 
To evaluate the PK of baloxavir marboxil after single-dose administration
 
	
 
Plasma concentrations of baloxavir marboxil (pro-drug) and S-033447 (active metabolite) will be summarized by time (<math>C_{24}</math> and <math>C_{72}</math>) and body weight
 
Population PK model derived parameters (e.g., <math>AUC_{inf}</math>, <math>C_{max}</math>, <math>T_{max}</math>, <math>t_{1/2}</math>) (modelling report)
 

Efficacy (Secondary) Objectives	Key Corresponding Secondary Endpoint

 
To evaluate the clinical efficacy of baloxavir marboxil compared with oseltamivir
 
	
 
Time to alleviation of influenza signs and symptoms, defined as the length of time taken from the start of treatment to the point at which all of the following criteria are met and remain so for at least 21.5 hours: 
 
A score of 0 (no problem) or 1 (minor problem) for cough and nasal symptoms (items 14 and 15 of the CARIFS)
 
A “yes” response to the following question on the CARIFS: “Since the last assessment has the subject been able to return to day care/school, or resume his or her normal daily activity in the same way as performed prior to developing the flu?”
 
First return to afebrile state (tympanic temperature <math>\leq 37.2^{\circ}\text{C}</math>)
 
 
 

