#### **2.2.1 Safety (Primary) Endpoints**

Incidence, severity, and timing of:

- Adverse events (AEs)
- Serious adverse events (SAEs)
- Vital sign measurements
- Clinical laboratory test results

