## 4.4 Visit Windows

**Table 2 Acceptable Time Windows for Parameters Other Than Data from the Patient Diary**

Time Point (Scheduled Time Point)	Acceptable Time Window
Pre-dose at Visit 1 (Day 1)	Before dosing on Day 1
Post-dose at Visit 1 (Day 1)	Between 0.5 and 4 hours after dosing (on Day 1)
Visit 2 (Day 2)	Day 2
Optional Visit 1 (Day 3)	Day 3
Visit 3 (Day 4)	Day 4
Visit 4 (Day 6)	Between Day 5 and Day 7 as follows: -if patient presents on Day 5 with no Day 4, and no Day 6 this will be classed as Visit 4 -if patient presents on Day 5 with no Day 4, and Day 6 this will be classed as Visit 3. -if patient presents on Day 5 with Day 4 and no Day 6 this will be classed as Visit 4.
Visit 5 (Day 10)	Between Day 8 and Day 12
Optional Visit2 (Day 15)	Between Day 13 and Day 22
Visit 6 (Day 29)	On or after Day 23
Withdrawal	Date of withdrawal + 14 days

\* if time is missing for data collected on Visit 1 where, per the schedule of activities, this data should be collected at 'v1 screening' or 'v1 post-dose' it is defined as 'Pre-dose at Visit 1 (Day 1)' or 'Post-dose at Visit 1 (Day 1)' respectively.

Measurements collected within the acceptable time window for each scheduled assessment time point, including data obtained at the time of withdrawal, will be used for the analyses of all endpoints at each assessment time point. For all patients with multiple values within a visit window, the value obtained closest to the target time point will be used. If two measurements collected with the same time deviation exist before and after the target time point, the measurement obtained before the target time point will be adopted for analysis. The assessment time point having no measurements within the corresponding acceptable time window will be considered as missing.

In the assessment of data from sources other than the patient diary, if there are multiple values which may be adopted for a scheduled assessment time point (even though the above rules have been strictly followed), the measurements at the time point entered in the Case Report Form (CRF) will be adopted.

For summaries of data not collected by visit, such as adverse events, medical history and concomitant medications, all data up to the last exposure date will be included.

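### Timing of adverse events is a named part of the primary safety endpoint, but SAP section 4.5.1 specifies no summary of it by onset

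*SAP*

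**What the plan says.** Protocol Table 1 gives the primary safety endpoint as "Incidence, severity, and timing of adverse events, serious adverse events, vital sign measurements, and clinical laboratory test results". SAP section 2.2.1 repeats the three attributes ("Incidence, severity, and timing of") and applies them to the same four items. SAP section 4.5 states the aim: "The primary objective for this study is to compare the safety of a single dose of baloxavir marboxil with 5 days of oseltamivir" given twice daily. Protocol section 6 says all analyses are descriptive and defers full details of tables, listings and graphs to the SAP.

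For adverse events, SAP section 4.5.1 plans the following:

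- "Adverse events will be coded and tabulated by SOC and/or PT".
- "Adverse events will also be tabulated by severity and relationship to the study drug as indicated by the investigator".
- Further summaries, introduced by "The following will also be summarized by treatment, and listings produced where required": serious events; events leading to withdrawal, to death, or to dose modification or interruption; and non-serious events at the 5% and 1% thresholds.
- Events of special interest by treatment group.

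Onset date appears in that section to decide whether an event is treatment-emergent: "Treatment-emergent events are defined as those AEs with observed or imputed onset date on or after the start date of trial treatment".

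On the data to be used, SAP section 4.4 says that for adverse event summaries "all data up to the last exposure date will be included". Protocol section 5.3.1 collects adverse events until 28 days after the last dose, and SAP section 2.4 bases the primary analysis on data to the Day 29 assessment.

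**The concern.** The protocol relies on the SAP to turn the primary endpoint into outputs. For adverse events and serious adverse events, incidence and severity become tables and timing does not. Someone who followed section 4.5.1 exactly would produce no by-arm summary of when events began or how long they lasted.

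The attribute matters in this design. One arm receives active drug once, on Day 1. The other receives ten active doses, the last on the evening of Day 5 or the morning of Day 6 (Protocol section 4.3.2.2). Whether events cluster around dosing or arise later is a natural part of comparing a single dose with a 5-day course, and frequency counts do not show it.

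**Working it through.** The point is a comparison of texts. Arithmetic is needed only for the cut-off and the expected counts.

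**1. The plan's own figure.** SAP Table 1 follows from 1 − (1 − p)^80. For p = 1% to 5% this gives 55.25%, 80.14%, 91.26%, 96.18% and 98.35%, against the stated 55.2%, 80.1%, 91.3%, 96.2% and 98.3%. The table is reproduced. It concerns whether an event occurs at all, so it neither supports nor weakens the point about timing.

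**2. Endpoint items against planned outputs.**

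| Item in the primary endpoint | Planned output in the SAP | Timing covered? |
|---|---|---|
| Adverse events | Counts by class/term, severity, relationship, consequence (4.5.1) | No |
| Serious adverse events | Counts by treatment (4.5.1) | No |
| Laboratory results | Values, changes and shifts by scheduled visit (4.5.3) | Yes |
| Vital signs | Values and changes by scheduled visit (4.5.4) | Yes |

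Protocol section 6.5 adds no timing analysis for adverse events. The gap is two of four items.

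**3. Are the data there?** Yes. Section 4.5.1 uses observed or imputed onset dates, SAP section 4.8 provides for partial dates, and Protocol section 5.5.1 requires resolution dates on the case report form.

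**4. Which days would a timing table cover?**

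- Oseltamivir arm: last active dose on Day 5 or 6.
- Baloxavir marboxil arm: last exposure on Day 1 if only active drug counts (SAP section 4.5.6 defines exposure there as 1 day), or Day 5 or 6 if the matching oseltamivir placebo counts.
- Collection period, last dose plus 28 days: 1 + 28 = Day 29, 5 + 28 = Day 33, or 6 + 28 = Day 34, depending on which dose is meant.
- Analysis cut in SAP section 2.4: the Day 29 assessment.

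Read literally, section 4.4 leaves any window starting on Day 7 empty in both arms. If only active drug counts as exposure, the baloxavir marboxil arm would also stop at Day 1 while the oseltamivir arm ran to Day 5 or 6.

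**5. How small would the counts be?** With 80 and 40 patients, a term at 5% is 0.05 × 80 = 4 and 0.05 × 40 = 2 patients. If both arms share a true risk p in a window, the 95% half-width for the difference is 1.96 × √[p(1 − p)/80 + p(1 − p)/40]. This gives 8.3 percentage points at p = 5%, 11.4 at 10% and 15.2 at 20%. These values of p are illustrative and do not come from the documents.

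**The case against.** The best case for leaving the SAP alone has three parts. First, the study is descriptive and tests nothing, so no inference depends on a timing table. Second, onset dates are collected and listings are allowed, so timing can be read patient by patient. Third, with 40 oseltamivir patients a split by onset will often describe two or three children.

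The first does not answer the point, because the missing output is itself descriptive and needs no test. The second stands only in part. Listings are produced where required and their content is not specified, and a listing is not a summary by arm when the objective is to compare. The third stands as a limit on detail: it argues for few, wide windows and against a median for every preferred term.

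A reader might also infer more than the documents support:

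- **That the arms cannot be compared on timing.** The dates exist. The plan simply specifies no such comparison.
- **That a whole third of the primary endpoint goes unreported.** Laboratory and vital-sign timing is covered, as are the incidence and severity of adverse events.
- **That background childhood illness in weeks 2 to 4 dilutes an early tolerability difference.** This needs adverse event summaries that run to Day 29, which SAP section 4.4 contradicts, and background rates that the documents do not give. A specific early event such as vomiting would also have its own preferred-term row, where unrelated later events could not mask it.

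**Conclusion.** The point holds in a confined form. Timing of adverse events and serious adverse events is part of the stated primary endpoint, and section 4.5.1 specifies no summary by onset day, onset period or duration. This is a mismatch between endpoint and analysis that should be corrected. It does not affect the validity of the trial, its sample size or any stated figure.

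The size is a missing output, not a bias that can be quantified. The conclusion rests on taking section 4.5.1 together with Protocol section 6.5 as the planned adverse event outputs, and on the protocol's statement that the SAP holds the full detail. The conflict over the adverse event cut-off is a separate inconsistency. It matters here because it decides whether a late onset window could contain any data.

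**What to change.** Add to SAP section 4.5.1 one descriptive table by arm: number and percentage of patients with any adverse event, and with any serious adverse event, by onset window. Day 1 – 2, Day 3 – 6 and Day 7 to end would serve; these cut-points are a suggestion and come from neither document. Define Day 1 as the first dose of any study drug and use identical windows in both arms. For the common preferred terms, add onset day and duration where counts allow.

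In the same amendment, reconcile SAP section 4.4 with Protocol section 5.3.1 and SAP section 2.4, so that adverse event summaries cover the full collection period in both arms. State whether matching placebo counts as exposure or study drug when those limits are set. Without this, the last row of the new table would be empty.

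The cost is SAP wording and one or two tables from dates already collected, with no new data, test or change in sample size. The downside is sparse cells, above all in the oseltamivir arm. Windows can be merged, and the table should be read as description only.

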#### **Adverse Events of Special Interest**

All adverse events of special interest (AESI) will be presented by treatment group. AESI include but are not limited to the following:

- Case of an elevated ALT or AST in combination with either an elevated bilirubin or clinical jaundice, as defined in protocol
- Suspected transmission of an infectious agent by the study drug

#### **4.5.2 Deaths**

Details of any deaths will be presented in the form of an individual patient listing, as well as a frequency table by treatment.

**Table 3 Pre-specified Abnormal Laboratory Criteria**

Term	Criteria
AST (U/L) or ALT (U/L) and Total bilirubin (mg/dL)	Meet all of the following criteria: 
 
• AST <math>\geq 3 \times</math> ULN or ALT <math>\geq 3 \times</math> ULN
 
• Total bilirubin Value <math>\geq 2 \times</math> ULN at same timepoint
 

ULN = upper limit of normal.

#### **4.5.4 Vital Signs**

For each of the vital signs (diastolic blood pressures, systolic blood pressures, respiratory rate and pulse rate), summary statistics of observation and the change from baseline will be presented by treatment group for each scheduled time point.

Baseline is defined as the last assessment prior to treatment.

#### **4.5.5 Body Temperature**

Body temperature is collected in the patient diary 4 times daily for Day 1 – 3, twice daily for Day 4 – 9 and once daily thereafter. Summary statistics of observation and the change from baseline in body temperature will be presented by treatment group for each recorded time point.

Baseline is defined as the first recorded assessment after treatment on Day 1.

#### **4.5.6 Exposure of Study Medication**

The duration of treatment exposure will be summarized with descriptive statistics by treatment group for the safety population.

The duration of treatment exposure [days] in the oseltamivir group is defined as the dosing period during which a patient takes medication as follows:

$$\{(final\ dose\ date) - (initial\ dose\ date) + 1\}$$

For the baloxavir marboxil group, duration of exposure is defined as 1 day if actual baloxavir marboxil granules for oral suspension are dosed.

The treatment compliance rate will be summarized with descriptive statistics by the treatment group for the safety population. In addition, the frequency and percentage of patients with compliance  $< 80\%$  and  $\geq 80\%$  will be presented.

The treatment compliance rate [%] in the oseltamivir group is defined as:

$$\frac{\text{actual frequency of treatment exposure}}{\text{expected frequency of treatment exposure}} * 100$$

For baloxavir marboxil group treatment compliance is defined as 100% if patients are dosed per protocol.

#### **4.6 EFFICACY ANALYSIS**

The statistical analyses of efficacy endpoints will be descriptive. The ITTi population will be used for all analyses. Additional analysis of efficacy analysis presenting the ITT population will not be completed.

The data will be summarized using means, standard deviations, medians, and ranges for continuous variables and proportions for categorical variables, as appropriate. Time-to-event endpoints and duration endpoints will be summarized using Kaplan-Meier plots and summaries of the median survival time. Summaries will be presented by treatment group.

Efficacy endpoints are based on the CARIFS questionnaire data which is recorded by parent/ caregiver using handheld device. This assessment data should be recorded for the following time periods:

Period	Time
Morning	0.500-10.59
Noon	11.00-14.59
Evening	15.00-18.59
Bedtime	19.00-23.59

\*data should not be recorded between 00.00 and 4.59.

In the case where the recorded time of an assessment is outside the period time window for that assessment, the end time of the period should be imputed as the assessment time.

In the case where the assessment time falls into the period between 00.00 and 4.59 (due to technical error) the assessment date will be imputed to the date prior to recorded assessment date and the assessment time will be imputed to the end time of the period time window.

The imputation method used in the derivation of time to alleviation of influenza signs and symptoms is described in Section 4.6.1. No further imputation methods will be used.

In all time to event analysis, patients who withdraw prior to event of interest will be censored at the last observation timepoint.

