#### **4.6.1            Efficacy Endpoints (Secondary Objectives)**

##### **Time to alleviation of influenza signs and symptoms**

Time to alleviation (TTAS) of influenza signs and symptoms in hours, will be summarized using descriptive statistics by treatment, as well as Kaplan-Meier plots. It is defined as the length of time taken from the start of treatment to the point at which all of the following criteria are met and remain so for at least 21.5 hours:

- A score of 0 (no problem) or 1 (minor problem) for cough and nasal symptoms (items 14 and 15 of the CARIFS questionnaire - see [Appendix 4](#))
- A “yes” response to the following question on the CARIFS: “Since the last assessment has the subject been able to return to day care/school, or resume his or her normal daily activity in the same way as performed prior to developing the flu?”
- First return to afebrile state (tympanic temperature  $\leq 37.2^{\circ}\text{C}$ ).

If a score of 4 (“do not know” or “not applicable”) occurs at any assessment during the study for items 14 or 15, the assessment will not be included in the calculation of the alleviation of symptoms because the assessment was unobservable.

Patients with symptom scores  $\leq 1$  for both items 14 and 15, as well as tympanic temperature  $\leq 37.2^{\circ}\text{C}$  and a “yes” response to the question ‘Since the last assessment has the subject been able to return to day care/school, or resume his or her normal daily activity in the same way as performed prior to developing the flu?’ at baseline will have a TTAS of all symptoms set to missing.

Patients who do not experience alleviation of symptoms prior to completion or withdrawal from study will be censored at the last observation time point.

Baseline is defined as the first CARIFS assessment after start of treatment on Day 1.

The number of patients with completed CARIFS as well as the number with missing CARIFS per assessment, will be presented by treatment. Additionally, the number and percentage of those with ‘Don’t Know/ Not Applicable’ per Question per assessment will be presented by treatment.

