d The parent/caregiver will assess and record in the patient diary, body temperature (tympanic assessment) four times daily (morning, noon, evening, and bedtime) from Days 1 to 3; twice daily (morning and evening) on Days 4 to 9; once daily on Days 10 to 15.

e The parent/caregiver will complete the CARIFS questionnaire twice daily (morning and evening) on Days 1 to 9 and then once daily on Days 10 to 15.

f Body weight and height will be measured on Days 1 and 29, only. Physical examinations on Days 2, 3, and 4 will be limited symptom-directed physical examinations and may be performed by a mobile nursing professional.

g Conduct assessment if the investigator determines that influenza symptoms or viral shedding are persisting or at the investigator's discretion.

h Vital signs will be recorded if abnormal physical examination findings or adverse events are recorded since last visit or at investigator's discretion on Day 29.

i At least two nasal and/or nasopharyngeal swabs (one for each nostril) to be taken at each visit.

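### SAP 4.6 overwrites out-of-window diary times and dates back all 00:00-04:59 stamps, including morning ones, which can reverse entries, put a post-dose entry before dosing and alter the 21.5 h hold

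*SAP*

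**What the plan says.** SAP section 4.6 divides the day into four diary periods: morning to 10:59, noon 11:00-14:59, evening 15:00-18:59 and bedtime 19:00-23:59. Nothing should be entered between 00:00 and 04:59. Two rules follow.

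- **Out-of-window rule.** An entry stamped outside its period loses its recorded time: "the end time of the period should be imputed as the assessment time". The window concerned is that of the entry's own period, since the rule applies where "the recorded time of an assessment is outside the period time window for that assessment".
- **After-midnight rule.** A stamp between 00:00 and 04:59, which the SAP attributes to technical error, has its clock time replaced by a period end: "the assessment time will be imputed to the end time of the period time window". Its date also goes back by one day: "the assessment date will be imputed to the date prior to recorded assessment date". No period is exempted, and the sentence does not say which period's window is meant.

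The section refers to 4.6.1 for the imputation used for time to alleviation and rules out any other. Section 4.6.1 covers don't-know answers, a baseline exclusion and censoring. It has no time rule that would correct these two, and no analysis on recorded times is planned.

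Three other statements depend on these times. Alleviation requires that "all of the following criteria are met and remain so for at least 21.5 hours". For time to alleviation, "Baseline is defined as the first CARIFS assessment after start of treatment on Day 1". Appendix 2 of the SAP has caregivers "complete the CARIFS questionnaire twice daily (morning and evening) on Days 1 to 9", so on those days CARIFS has no noon or bedtime slot.

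**The concern.** The endpoints are measured in hours from the start of treatment and depend on a hold of 21.5 h, so the placement of single entries matters. Moving the date back makes sense for an evening or bedtime entry completed after midnight. It does not make sense for a morning entry made shortly before 05:00, which would be placed on the previous morning. The out-of-window rule also affects entries with no clock fault: an evening CARIFS completed at 20:00 is simply late, yet its recorded time is discarded.

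Three results could be wrong: the order of a child's entries, whether an entry counts as post-treatment (and so can be the baseline), and whether a hold counts as met. Time to alleviation is the key secondary endpoint, and duration of symptoms also uses CARIFS times. Whether the rules extend to the temperature diary, and so to duration of fever, is not stated. The four periods match the four-times-daily temperature schedule, but the text names only CARIFS.

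**Working it through.** The plan gives no figure on this point, so there is none to reproduce. The check applies the two rules to example stamps.

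**Inputs.** Period windows: SAP 4.6 (the morning start has a misplaced point and is read as 05:00). Hold of 21.5 h and the baseline definition: SAP 4.6.1. CARIFS morning and evening on Days 1 to 9: SAP Appendix 2. First doses after 16:00 are foreseen: Protocol 4.3.2.2. Assumptions: an entry keeps its scheduled label (morning or evening), and a hold is judged by the gap between its first entry and a later one, with all entries between also alleviated.

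**Step 1: after-midnight rule.** Shift = imputed time minus recorded time.

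| Period end used | Imputed to, previous day | Shift of a 00:00 stamp | Shift of a 04:59 stamp |
|---|---|---|---|
| Morning | 10:59 | -13.02 h | -18.00 h |
| Evening | 18:59 | -5.02 h | -10.00 h |
| Bedtime | 23:59 | -0.02 h | -5.00 h |

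The 18 h figure needs the entry's own period to be the window meant. If bedtime is meant for every such stamp, the maximum is 5 h.

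**Step 2: order of entries (own-period reading).** A Day 2 morning entry stamped 04:50 becomes Day 1, 10:59. A Day 1 evening entry at 17:00 stays where it is. As recorded, the morning entry comes 11 h 50 min after the evening one. As imputed, it comes 6 h 01 min before it. If the first dose was after 10:59 on Day 1, it also precedes treatment.

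**Step 3: late evening entry (out-of-window rule).** First dose 19:30, evening CARIFS 20:00. Recorded: 30 min after dosing. Imputed to 18:59: 31 min before dosing. The same happens for any first dose after 18:59, because every later evening entry that day is set to 18:59.

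**Step 4: the 21.5 h hold.**

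| First entry | Later entry, next day | Recorded gap | Imputed gap |
|---|---|---|---|
| Evening 20:30 (to 18:59) | Evening 17:00 (unchanged) | 3.5 + 17.0 = 20.5 h, not met | 5 h 01 min + 17 h = 22.0 h, met |
| Evening 14:50 (to 18:59) | Evening 15:10 (unchanged) | 24 h 20 min = 24.33 h, met | 5 h 01 min + 15 h 10 min = 20.18 h, not met |
| Morning 07:00 (unchanged) | Morning 04:50 (to 10:59 the day before) | 21 h 50 min = 21.83 h, met | 3 h 59 min = 3.98 h, not met |

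The first two rows need only the out-of-window rule. The third also needs the own-period reading of the after-midnight rule.

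**Step 5: effect on the event time.** The event time is the start of the hold. In the first row, suppose the child is still alleviated at 07:00 on the following morning. The recorded gap from 20:30 is then 34.5 h, so the hold is met either way. The event time is 20:30 recorded or 18:59 imputed, a difference of 1 h 31 min. Only a relapse at that next entry makes the two versions disagree on whether the event occurred. In general the event time moves by the shift of the entry that opens the hold: up to 5.0 h earlier for an evening entry stamped 19:00-23:59, and 4 h 09 min later for the 14:50 entry in the second row.

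**The case against.** The strongest reply has four parts.

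**The stamps are already suspect.** The SAP calls 00:00-04:59 stamps technical errors, so a distance from such a stamp is not a distance from the true time. It also never says that morning entries are moved, and dating back fits late entries best. This stands in part. A reader might infer that the plan misplaces entries by 18 h as a fact. The documents support only a literal reading with that result, beside another with a maximum of 5 h. An unreliable stamp still gives no reason to put a morning entry on the previous morning.

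**A changed hold seldom changes the endpoint much.** This stands, as step 5 shows. A reader might infer large errors in time to alleviation. Under the out-of-window rule, disagreement over whether a hold counts needs a relapse at the confirming entry.

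**Losing a baseline seldom matters.** A time to alleviation is set to missing only if cough, nasal symptoms, temperature and activity are all already satisfactory at baseline, and entry requires fever of at least 38°C. The other CARIFS use is in the individual symptom durations, which are supportive. The SAP also does not say that imputed times decide what is post-dose. This stands. A reader might infer that children treated in the evening drop out of the analysis, but the documents do not say so.

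**The stakes are low.** Efficacy is secondary and descriptive, the rules are the same in both arms, and the time rule was added deliberately by SAP amendment. This also stands. No test or error rate is affected, and nothing here shows bias between arms. It does not make the wording right.

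**Conclusion.** The point holds as a defect in a stated rule that should be corrected, with limited consequences. As written, the SAP can reverse the order of entries, place an entry made after dosing before it, and create or remove a 21.5 h hold.

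The sizes are conditional. The after-midnight shift is 13.02 to 18.00 h for a morning entry if its own period is meant, and at most 5 h if bedtime is meant. The loss of a post-treatment baseline applies to first doses after 18:59 and assumes that imputed times decide. Where a hold is confirmed either way, the event time moves by the shift of one entry, about 1.5 h in the 20:30 example.

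The documents do not say how many entries fall outside their windows, so no effect on a median or on the difference between arms can be given. Nor do they support using recorded device times for everything in the main analysis, because some of those stamps are presumed faulty.

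**What to change.** 1. Limit the previous-date rule to evening and bedtime entries, and state which period's end time is used. Do not move morning entries to the previous day.
2. Do not impute a time before the first dose for an entry recorded after it. Use the recorded time to decide whether an entry is post-dose for the baseline definition.
3. Add a sensitivity analysis of time to alleviation and the duration endpoints on recorded device times. List the 00:00-04:59 stamps and flag them as suspected clock errors.

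The same edit should say whether the rules cover temperature entries. The cost is a few sentences in SAP 4.6, a small amount of extra programming and one listing. No data collection changes.
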